3.1 Overall Design

This single site, NIH Stage I of Behavioral Intervention Development trial will extend principles of subject-centered care (a pillar of caring for older adults with MCC) to medication management by producing a broadly applicable approach (N-of-1) that can bypass the inherent limitations of randomized controlled trials which provide average treatment effects and limited data on the effects of medication for a single individual; and thereby facilitate personalized pharmacotherapy and therapeutic precision by determining the optimal therapy for the individual in the face of the inherent complexity and heterogeneity of older adults related to variability in clinical phenotype, drug metabolism, responsiveness to therapy, and health priorities.

This study will also formalize a process that can increase subject involvement and incorporate shared decision making into medication management, an important priority in cardiovascular medicine.

We will conduct N-of-1 trials using a two-arm crossover withdrawal/reversal design (On [A] vs Off [B]) with up to 4 periods. Subjects will be randomized to either Arm1/ABAB or Arm2/BABA (see Figure 1 above). After the initial period (Period 1), each subject will crossover to the other arm and continue in that arm for up to 6 weeks (Period 2). This may be repeated for two more periods for a total of 4 periods; each period will last up to 6 weeks, permitting sufficient time for up-titration and onset of drug action, and down-titration and washout. If the subject and the principal investigator make a final decision to discontinue or continue the beta-blocker at the end of a period, the end of intervention phase will begin at the end of that period visit. For the remainder of the protocol, we refer to “end of intervention” as period 4, but this can be changed based on when a final decision is made about the beta-blocker. The end of intervention visits can occur at any of the periods. The minimum number of periods will be 2 (AB or BA). If the subject wishes to collect more data, then additional periods may be added in an alternating fashion (ABAB or BABA). Accordingly, the number of periods will be an adaptive component of the protocol.

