8.1 Discontinuation of Study Intervention

If consented subjects are intolerant or unwilling to proceed with dose modification, we will continue to follow them through the course of the study (if subject is willing). Remaining study procedures will be completed as indicated by the study protocol. If a clinically significant finding is identified (including, but not limited to changes from baseline) after enrollment, the investigator will determine if any change in subject management is needed. Any new clinically relevant finding will be reported as an adverse event (AE).

The data to be collected at the time of study intervention discontinuation will include the following:

- Concomitant Medications
- Decision making outcomes questionnaire
- Short Physical Performance Battery
- Adverse Events/SAE

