8.2 Subject Discontinuation/Withdrawal from the Study

Subjects are free to withdraw from participation in the study at any time if they wish.

An investigator may discontinue or withdraw a subject from the study for the following reasons:

- Pregnancy
- Significant study intervention non-compliance
- If any clinical adverse event (AE), or other medical condition or situation occurs such that continued participation in the study would not be in the best interest of the subject (this will be decided on conjunction with their own physician and/or the DSMB).
- Disease progression which requires discontinuation of the study intervention
- If the subject meets an exclusion criterion (either newly developed or not previously recognized) that precludes further study participation
- Subject lost to follow-up after several attempts to contact subject to schedule study visit.

The reason for subject discontinuation or withdrawal from the study will be recorded on the Case Report Form (CRF) in REDCap. Subjects who sign the informed consent form and are randomized but do not receive the study intervention may be replaced. Subjects who sign the informed consent form, and are randomized and receive the study intervention, and subsequently withdraw, or are withdrawn or discontinued from the study, will be replaced.

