13.3 AE/SAE Follow Up

In addition to reporting all adverse events, the study team will take all appropriate measures to ensure that subjects will have access to necessary medical care. Any acute change in medical condition will be reported to the subject's physician for follow-up care. All information about the study will be provided to the caring physician. As this study is not blinded, there will be no masking issue with regard to providing optimal medical care. All study procedures will be discontinued at the treating physician's request, the subject's request, and/or as judged appropriate by the principal investigator. In the case of any emergency situation, the study physicians will institute any emergency aid needed and then make arrangements for transportation to the Emergency Department. All research subjects will have access to medical care if an adverse event occurs. The subject and/or the insurance carrier will be billed for this care. Subjects will not receive special compensation for injury solely because they are subjects in the study. All subjects are fully informed about this policy as part of the informed consent process.

For SAEs that are determined to be “possibly related” or “related”, the subject will be assessed, evaluated, and treated for any potential recurrence and according to the seriousness of the symptoms. Based on the information gathered, it will then be determined whether the subject should be removed from the study or continue their participation.

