13.4 Time Period and Frequency for Event Assessment and Follow Up

The occurrence of an adverse event (AE) or serious adverse event (SAE) may come to the attention of study personnel during study visits and interviews of a study subject presenting for medical care, or upon review by a study monitor.

All AEs including local and systemic reactions not meeting the criteria for SAEs will be captured on the appropriate case report form (CRF). Information to be collected includes event description, time of onset, clinician's assessment of severity, relationship to study product (assessed only by those with the training and authority to make a diagnosis), and time of resolution/stabilization of the event. All AEs occurring while on study must be documented appropriately regardless of relationship. All AEs will be followed to adequate resolution.

Any medical condition that is present at the time that the subject is screened will be considered as baseline and not reported as an AE. However, if the study subject's condition deteriorates at any time during the study, it will be recorded as an AE.

Changes in the severity of an AE will be documented to allow an assessment of the duration of the event at each level of severity to be performed. AEs characterized as intermittent require documentation of onset and duration of each episode.

The study coordinator or the principal investigator will record all reportable events with start dates occurring any time after informed consent is obtained until 7 (for non-serious AEs) or 30 days (for SAEs) after the last day of study participation. At each study visit, the investigator will inquire about the occurrence of AE/SAEs since the last visit. Events will be followed for outcome information until resolution or stabilization. The following table provides examples of actions that may be taken following selected adverse events.

| Adverse Event | Typical Action |
|----------------------------|---|
| Hospitalization | Medical management including beta-blocker management as recommended by treating physician. If hospitalization unrelated to study and not contraindicated following discussion between investigators and hospital care team, subject will continue to follow protocol while hospitalized. |
| Worse or new arrhythmia | Emergent care if indicated including admission and necessary medications/interventions. Subject withdrawal from the study. |

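### After arrhythmia, stroke, MI or angina, the typical action in 13.4 is withdrawal from the study rather than from the intervention, and 8.2 replaces such subjects without providing for their continued follow-up

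*Combined protocol and SAP*

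**What the plan says.** The table in section 13.4 pairs eight adverse events with a typical action. For new or worse arrhythmia, stroke, MI and angina the entry is the same: "Emergent care if indicated including admission and necessary medications/interventions. Subject withdrawal from the study". The table is introduced as illustrative: "The following table provides examples of actions that may be taken following selected adverse events". The same section records events with onset "until 7 (for non-serious AEs) or 30 days (for SAEs) after the last day of study participation", and follows recorded events until they resolve or stabilize.

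Section 8.1 deals with stopping the intervention. It says that for subjects "intolerant or unwilling to proceed with dose modification, we will continue to follow them through the course of the study", provided they are willing.

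Section 8.2 deals with leaving the study. An adverse event can be grounds for withdrawal, and "this will be decided on conjunction with their own physician and/or the DSMB". The reason goes on the case report form. Subjects who are "randomized and receive the study intervention, and subsequently withdraw, or are withdrawn or discontinued from the study, will be replaced".

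Section 13.3 adds that, after a related or possibly related SAE, "it will then be determined whether the subject should be removed from the study or continue their participation".

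Sections 6.1.3 and 7.7 set reviews at 6, 9 and 12 months after the end of intervention. Between them these cover vital status, hospitalizations, emergency visits, beta-blocker use, questionnaires and a call. Section 3.1 describes how the end of intervention is reached: once a final beta-blocker decision is made at the end of a period, "the end of intervention phase will begin at the end of that period visit".

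**The concern.** Stopping study dose changes after any of these four events is clinically sensible. Ending observation as well is a separate decision, and the plan needs to keep the two apart. Section 8.1 does so for subjects who cannot tolerate or do not want further dose changes. The four table rows do not, because they name the study and not the intervention as the thing the subject leaves.

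All four events are on the plan's own list of risks of tapering or stopping a beta-blocker (section 2.3.1, item i). What happens to these subjects afterwards, including whether they die, are admitted or go back on a beta-blocker, is information that a larger discontinuation trial would want. Section 12 says these data are meant to help prepare such a trial. The subjects harmed during the intervention are the ones whose later course the plan leaves without stated follow-up.

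**Working it through.** No figure in the plan is at issue, so the check is a comparison of the texts.

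1. **Is the withdrawal entry only loose wording for stopping the drug?** Compare the eight rows of the 13.4 table. The rows for hospitalization, heart failure exacerbation, shortness of breath and worsened hypertension each keep a route to staying on protocol if the event is unrelated to the study and the physicians agree. The four rows in question have no condition and no route to observation without dose changes. The table therefore does separate staying from leaving, and for these four events its typical action is leaving.

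2. **Does the follow-up in 8.1 reach these subjects?** Section 8.1 covers intolerance of, or unwillingness to proceed with, dose modification. It lists data to collect when the intervention stops (medications, decision questionnaires, the physical performance battery, adverse events). Section 8.2 covers withdrawal from the study and has no matching sentence: it asks for the reason and provides for replacement. Nothing carries the 8.1 follow-up over to a subject withdrawn under 8.2 or 13.4.

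3. **What safety capture remains for a withdrawn subject?** The index event is followed until it resolves or stabilizes (13.4), and all AEs and SAEs go to the DSMB (section 15). New SAEs are recorded for 30 days, and new non-serious AEs for 7 days, after the last day of participation. The first scheduled review is at 6 months. A new death or admission after day 30 would be picked up systematically only if the subject is included in the 6-, 9- and 12-month reviews.

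4. **Is the subject included in those reviews?** Sections 6.1.3 and 7.7 neither include nor exclude withdrawn subjects. Both count from the end of intervention. Section 3.1 describes that point through a final decision at an end-of-period visit, and otherwise refers to it as period 4. A stop in the middle of a period, for example after an MI, is not addressed.

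The result is that ending participation is the stated typical action for the four events, replacement follows, and later follow-up is not provided for in the text.

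**The case against.** The strongest reply is that the table binds nobody. It offers examples, 13.3 decides removal case by case after a related or possibly related SAE, and 8.2 brings in the subject's physician and/or the DSMB. A subject with angina during a taper could fairly be called intolerant of dose modification and so be covered by 8.1. Several of these events also match exclusion criteria (angina, recent MI, ventricular tachycardia), and 8.2 allows withdrawal when one newly develops. The listed risks are qualified in 2.3.1 as shown with abrupt cessation, whereas this plan tapers. All of this stands and limits the weight of the point. It does not remove it, because case-by-case removal still leaves unsaid what follow-up a removed subject receives.

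Three stronger readings are tempting, and the documents do not support them.

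- A reader might infer that the plan shuts these subjects out of the 6-, 9- and 12-month review. It does not; it is silent.
- A reader might infer that their review cannot be started for want of a date. Section 3.1 does not say that intervention can end in no other way, and 8.1 already uses the time of intervention discontinuation as a data point, so a workable date exists and only needs stating.
- A reader might set the 30-day window against twelve months and quote a share of follow-up lost. That presupposes that the review does not apply, and it treats three scheduled reviews as continuous surveillance.

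**Conclusion.** The point holds as a minor, inexpensive improvement to safety follow-up. For four events on the plan's own risk list, the typical action is to leave the study, and 8.2 replaces such subjects without providing for continued follow-up. The possible loss is of later deaths, admissions and beta-blocker status. It arises only if the typical action is followed and the later review is not applied to withdrawn subjects.

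No number can be put on the loss. The documents give no rate for these events; the absence of SAEs in 9 prior N-of-1 trials (section 3.1) does not supply one. Recording of the index event is not in doubt, and no listed endpoint, sample size or analysis changes.

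**What to change.** In the four rows of the 13.4 table, replace the withdrawal sentence with: *permanent discontinuation of the study intervention (no further study dose changes, CPET or other exercise testing); safety follow-up continues unless consent is withdrawn*. The exclusion of exercise testing should be explicit. A bare reference to 8.1 would bring in the remaining study procedures, which can include CPET, and that is not suitable after an MI.

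Add to 8.2: *treated subjects whose study intervention is stopped for an adverse event, including those who are replaced, remain in the 6-, 9- and 12-month health-record review and calls, timed from the date the study intervention stopped*.

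The cost is wording in four table cells and a sentence in 8.2, plus a few extra record reviews and calls using procedures already planned in 6.1.3 and 7.7.

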14.1 Definition of Unanticipated Problems Involving Risks to Subjects or Others (UPIRTSO)

[The Office for Human Research Protections (OHRP) considers unanticipated problems involving risks to subjects or others to include, in general, any incident, experience, or outcome that meets all of the following criteria:

- Unexpected in terms of nature, severity, or frequency given (a) the research procedures that are described in the protocol-related documents, such as the Institutional Review Board (IRB)-approved research protocol and informed consent document; and (b) the characteristics of the subject population being studied;
- Related or possibly related to participation in the research (“possibly related” means there is a reasonable possibility that the incident, experience, or outcome may have been caused by the procedures involved in the research); and
- Suggests that the research places subjects or others at a greater risk of harm (including physical, psychological, economic, or social harm) than was previously known or recognized.

14.1.2 Unanticipated Problem Reporting

The investigator will report unanticipated problems (UPIRTSOs) to the reviewing Institutional Review Board (IRB). The UPIRTSO report will include the following information:

- Protocol identifying information: protocol title and number, PI’s name, and the IRB project number;
- A detailed description of the event, incident, experience, or outcome;
- An explanation of the basis for determining that the event, incident, experience, or outcome represents an UPIRTSO;
- A description of any changes to the protocol or other corrective actions that have been taken or are proposed in response to the UPIRTSO.

To satisfy the requirement for prompt reporting, UPIRTSOs will be reported using the following timeline:

- UPIRTSOs that are serious adverse events (SAEs) will be reported to the IRB and to the DSMB within 3 days of the investigator becoming aware of the event.
- Any other UPIRTSO will be reported to the IRB and to the DCC/study sponsor within 7 days of the investigator becoming aware of the problem.

15. Data and Safety Monitoring Plan (DSMP)

We plan to use the WCM DSMB for this trial, as this a resource provided to the WCM scientific community, and they have the necessary expertise and infrastructure to act as a DSMB for this trial. All AEs and SAEs will be reported to the DSMB. AEs where the harm is unexpected, the harm is “related” or “possibly related,” and the harm suggests that the research places subjects at greater risk of harm than previously known, an immediate report will be submitted within 7 calendar days of the PI awareness. We will record seriousness, relatedness and expectedness of the adverse event, as determined by [name]. We will

report when the AE occurred, as well as when the study team became aware of the AE. We will collect any medical documentation pertaining to the AE. If treatment must be stopped, this determination will be made by [name] with the subject. Because all subjects will have been on study drug before initiating the trial, and we will not exceed their home dose, we do not anticipate having to terminate study treatment.

The DSMB will convene to review the study data after each cohort of 4 subjects.
